The primary outcome is OCD severity as assessed by the blind rater-administered Yale-Brown Obsessive-Compulsive Scale (Y-BOCS). Specifically, we will test whether B4DT is non-inferior to

standard CBT 14 weeks after treatment start. The non inferiority margin is set to 4 points on the Y-BOCS.

Non-inferiority designs test whether a novel treatment is not unacceptably less efficacious (in this case, 4 points) than another treatment whose efficacy has already been established. However, a non-inferiority study may also be used to test for superiority without inflating the false-positive rate [7]. We will therefore sequentially test 1) whether B4DT is non-inferior to gold standard CBT , and 2) whether B4DT is superior to gold standard CBT.

Secondary outcomes

Our secondary objectives are to compare B4DT and gold standard CBT with regards to:

- 1) Time to response. We hypothesize that B4DT, due to its intensive design, will provide a faster response than gold- standard CBT. A comparison of the proportion of treatment responders at week 4 and week 7 will be used to test this hypothesis.
- 2) Rates of response and remission. The proportion of participants in response and remission will be compared 14 weeks after treatment start. For these outcomes, we have no directed hypotheses.
- 3) Dropout rate. We will test whether the proportion of patients that discontinue treatment prematurely (i.e., complete less than 50% of the treatment) differs between the B4DT and the gold standard CBT arm. For this outcome, we have no directed hypothesis.
- 4) Cost-effectiveness. Health economic data will be collected using clinic data on therapist usage and the Treatment Inventory of Costs in Psychiatric Patients [11]. Between-group costs will be calculated and compared 14 weeks after treatment start. The emphasis will be on cost-effectiveness analyses using responder status as outcome and health-care provider as the cost perspective. For this outcome, we have no directed hypothesis.
- 5) Negative effects. The total score of the Negative Effects Questionnaire will be compared 14 weeks after treatment start, as well as the prevalence of severe adverse events. For this outcome, we do not have a directed hypothesis.

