If a participant expresses suicidal ideation during treatment or at subsequent assessments, assessors will initiate a structured suicide risk assessment in accordance with routines at the clinic. If there is an urgent need for psychiatric care, a trial psychiatrist will contact participants to schedule an appointment as soon as possible. Serious adverse events (e.g., urgent psychiatric care or discontinued treatment due to a worsening of psychiatric symptoms) will be described in detail on a case-by-case basis.

Statistical analysis

All analysis scripts have been uploaded to a public repository with the analysis strategies described in detail using simulated data (<https://osf.io/w5bfp/>).

Primary outcome

Y-BOCS

The primary non-inferiority hypothesis on the clinician-rated Y-BOCS will be evaluated using ANCOVA of group differences at post-treatment with pre-treatment score as covariate. It will be based on participants that have received at least 50% of the treatment (i.e., attended at least 8 sessions of individual CBT or 1.5 days of B4DT) and completed the post treatment assessment 14 weeks after treatment start. This per protocol approach is chosen to avoid potential problems related to study design that can bias the results towards the alternative hypothesis of non-inferiority (the opposite is true in superiority trials). No data imputation will be conducted at this stage. A 95% confidence interval will be used to model the gold standard CBT-B4DT effect. Non-inferiority will be considered supported if the upper bound is less than 4 (the non-inferiority margin) and superiority will be considered supported if the upper bound is less than 0. This testing procedure has the Type I error rate controlled at the 2.5% level for both comparisons.

For sensitivity assessment, the same ANCOVA model will be used again but with an intention to treat approach. Missing data will then be estimated using maximum likelihood after which the models are refitted. The aim of these steps is to address the potential influence of non-random missing data in the primary per protocol analysis.

Non-inferiority margin

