Although there are no strict guidelines regarding the selection of non-inferiority margins, half the placebo-controlled effect of gold-standard treatment is often recommended as adequate [23]. The proposed non-inferiority margin of 4 is smaller than half of the 10-point effect for ERP on the Y-BOCS [4], and would therefore be a stringent non-inferiority margin. Moreover, a non-inferiority margin of 4 points gives similar precision compared to previous non-inferiority trials for OCD in adults that have used 5 points [19] or 3 points [20], and a previous non-inferiority trial in pediatric OCD that used a margin of 4 points [30]. From a clinical point of view, a 4-point margin on the Y-BOCS is considered a small but observable difference in OCD symptoms.

Secondary outcomes

While this study was designed to have high power to assess the primary hypothesis, we do not have sufficient power to robustly compare the secondary outcomes between the treatment arms without inflating the false positive rate. This means that the results from these analyses should be interpreted with caution. On secondary outcomes, our approach will be to compute 95% confidence intervals of group differences without comparing the bounds to any predefined margin. Because the non-inferiority testing procedure will not apply, the secondary outcomes will be analyzed using an intent to treat approach including all randomized participants.

Moreover, we do not plan to collect data continuously throughout the treatments since our focus is on the pre-post comparisons. This decreases the usefulness of statistical methods that make imputations based on past observations. Therefore, unless the proportion of missing data exceeds 10%, no data imputation methods will be used as default (unless stated otherwise). However, if the proportion of missing data exceeds 10%, we will perform maximum likelihood imputations based on demographics and the scores from the pre-treatment assessment to complement the complete case analyses. The implications of these analyses on the reliability of the results will be discussed.

Time to response

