All patients will get either gold standard CBT or B4DT delivered by clinicians who are specialized in each of these forms of treatment delivery. Gold standard CBT is already the firsthand choice for this patient group, and its efficacy and safety has been demonstrated by several studies of high quality [4]. While B4DT has not yet been evaluated in an RCT with an active control group, it is an intensive face-to-face treatment built on ERP. Moreover, uncontrolled studies have suggested that the effect is similar or improved compared to gold standard CBT [6]. We therefore consider the additional risks associated with participating in the B4DT-arm to be small. All participants will be monitored closely during the study and additional treatment will be provided in case of severe deterioration. Such decisions will be made on a case-by-case basis by the clinicians. This means that if a patient becomes significantly worse during treatment, he/she will be handled in the same way as the regular patients at the clinic.

The requirement to travel to another specialist clinic within Stockholm may put a strain on some participants who have financial or mobility difficulties or simply do not wish to travel. Participants referred to the clinics by other health-care services and who decline participation in the trial or turn out not to be eligible, will have an equal chance to receive specialist treatment at the clinic they were assessed. Excluded self-referred participants will be guided to adequate care.

Maximizing knowledge gain and minimizing risk of bias

Systematic evaluations of clinical trials have in recent years highlighted limitations in current practice that bias the scientific literature [14, 15, 16, 17]. As researchers and other stakeholders have begun to acknowledge the need to better control different sources of bias, the interest in issues related to replicability, transparency, and error control have grown substantially in

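### Is the direction of the primary non-inferiority contrast left open, so that the test could be run backwards?

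*Combined protocol and SAP*

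**What the plan says.** The decision rule is in the section Statistical analysis, Primary outcome, Y-BOCS. The model is an "ANCOVA of group differences at post-treatment with pre-treatment score as covariate". The interval is described as follows: "A 95% confidence interval will be used to model the gold standard CBT-B4DT effect". The rule then reads: "Non-inferiority will be considered supported if the upper bound is less than 4 (the non-inferiority margin"). Superiority is supported if the same upper bound is below 0. The paragraph closes its account of the test with: "This testing procedure has the Type I error rate controlled at the 2.5% level for both comparisons".

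The direction of the hypotheses is set under Research questions, Primary outcome. B4DT is tested first for non-inferiority to CBT and then for superiority over CBT. That section says such designs test whether "a novel treatment is not unacceptably less efficacious (in this case, 4 points) than another treatment" of established efficacy.

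The Statistical analysis section also says: "All analysis scripts have been uploaded to a public repository with the analysis strategies described in detail using simulated data". Those scripts are not part of the documents reviewed here.

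**The concern.** No sentence writes the contrast as a subtraction or says what a positive value means. The model is described on post-treatment Y-BOCS, where lower is better (remission requires a score of 12 or less). If the hyphen in the label is read as a minus sign between adjusted scores, a positive value means that CBT patients ended with more symptoms, which favours B4DT. Requiring the upper bound to stay below 4 would then limit how much better B4DT may be. Requiring it to fall below 0 would show that B4DT is worse. Both confirmatory conclusions would be reversed and the 2.5% error rate would be lost. This is the trial's only confirmatory rule, so the question deserves a check.

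**Working it through.** **Inputs.** The section Sample size calculation gives 60 per arm, 10% missing (60 × 0.9 = 54 evaluable per arm), a pre-treatment mean of 22.6 (SD 3.78), and a CBT post-treatment mean of 12.9 (SD 4.07). The margin is 4. Two inputs are not given and are assumed: the B4DT post-treatment SD (set to 4.07) and the pre-post correlation r (0 to 0.5).

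**Notation.** D is the true adjusted mean Y-BOCS, B4DT minus CBT, so positive means B4DT is worse.

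SE = 4.07 × √(1 − r²) × √(2/54) = 0.783 (r = 0), 0.747 (r = 0.3), 0.678 (r = 0.5).

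At r = 0 the half-width of the 95% interval is 1.96 × 0.783 = 1.535.

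**The plan's own power figure.** At D = 0, power is Φ((4 − 1.535)/0.783) = Φ(3.147) = 99.9%, consistent with the stated figure of over 95%. By symmetry both readings give this value, so the power statement cannot show which was meant.

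**The two readings at r = 0 (normal approximation).**
- Reading A (B4DT minus CBT in scores): non-inferior if estimate + 1.535 < 4, superior if estimate + 1.535 < 0.
- Reading B (CBT minus B4DT in scores): the same rules applied to the estimate with its sign changed.

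| True D | A: non-inferior | A: superior | B: non-inferior | B: superior |
|---|---|---|---|---|
| +4 | 2.5% | 0.0% | 100.0% | 99.9% |
| 0 | 99.9% | 2.5% | 99.9% | 2.5% |
| −3 | 100.0% | 96.9% | 24.7% | 0.0% |

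Simulated ANCOVA with t-based intervals (20,000 datasets per cell; r = 0, 0.3, 0.5) agrees. At D = +4, non-inferiority is declared in 2.6%, 2.4% and 2.4% under A, against 100% under B. At D = 0, the two non-inferiority verdicts differ in 0.22%, 0.13% and 0.02% of datasets.

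**Which reading the text allows.**
1. Superiority means that B4DT is better than CBT, and it is claimed when the whole interval is below 0. Negative values therefore favour B4DT, and on a scale where lower is better that is Reading A.
2. The margin is introduced as the amount by which the novel treatment may be less efficacious. An upper limit of +4 is that amount only under A.
3. The 2.5% error rate is claimed for both comparisons. Under A it holds at each null boundary (D = +4 for non-inferiority, D = 0 for superiority) and the error is smaller further into the null. Under B, a B4DT that is 4 points worse passes non-inferiority in 100% of trials and superiority in 99.9%.
4. The documents use the word effect to mean benefit. The section Non-inferiority margin refers to "half of the 10-point effect for ERP on the Y-BOCS", and Patient safety says that "uncontrolled studies have suggested that the effect is similar or improved compared to gold standard CBT". CBT benefit minus B4DT benefit is B4DT's deficit, so even a literal minus sign leads to Reading A.

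**Equivalence of benefit and score.** Let the reduction be pre minus post. With the pre-treatment score as covariate, the group coefficient for the reduction is the negative of that for the post score. Hence the adjusted CBT minus B4DT reduction equals the adjusted B4DT minus CBT post score. In the simulated datasets the largest gap was below 1e-13.

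**The case for a change.** The strongest case for a change is that a confirmatory cut-off is not fully specified until its sign is written, in a plan that makes a priority of preregistered analyses. The paragraph describes a model for scores, not benefit, so score subtraction is a natural first reading. The consequence of that reading is total and does not depend on the assumed SD: with SD 6.0, Reading B still declares non-inferiority in 100% of trials at D = +4. The Limitations section aims to keep statisticians blinded, which might make a written direction more important. One sentence would cost nothing.

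It is true that the subtraction is not written out, and the label alone can be misread. The rest does not show a defect. The sign follows from the superiority rule and the stated hypothesis, without any appeal to the label. An analyst who adopted Reading B would have to call B4DT superior when its scores were clearly higher, against the trial's own hypotheses. Masking does not alter this: a directional rule about B4DT cannot be applied until the arms are identified, however the formula is written. The posted scripts may show the arm coding, but the argument here does not rely on them.

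**Conclusion.** The concern does not call for a change. The contrast is not printed as a formula, but the rule fixes its direction: positive values mean B4DT is worse, +4 is its largest tolerated deficit, and an interval wholly below 0 shows B4DT superior. Followed in that way, the plan gives 2.5% Type I error for both comparisons and about 99.9% power with no true difference. Spelling out the subtraction would leave the model, margin, bounds, sample size and conclusions as they are.

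The contrast of about 100% with 2.5% arises only under a reading that the plan's own hypotheses and error statement rule out. Even then, in the planning case of no true difference, the two non-inferiority verdicts would differ in about 0.2% of trials or fewer. The percentages assume SD 4.07 in both arms, 54 evaluable per arm and r between 0 and 0.5. The conclusion about direction rests on the text and needs none of these assumptions.

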This study was designed to have high power to test the primary hypothesis, that B4DT is non-inferior to gold standard CBT using a 4-point margin on the Y-BOCS. However, this study is not sufficiently powered to make confirmatory claims based on the results of the secondary analyses. This means that the results will be interpreted as explanatory (despite the fact that 95% confidence intervals of group differences will be reported to follow common practice in the field).

Methods

Study Design

We will conduct a single-blind (blinded outcome assessors), randomized (1:1), controlled non-inferiority trial comparing intensive 4-day CBT and gold-standard individual CBT for adults with OCD. The total number of participants will be 120 (60 per group). Participants will be assessed before treatment start, at week 4 and 7, 14 weeks after treatment start (primary end-point), and 7- and 16-months after treatment start (follow-ups). The Consolidated Standards of Reporting Trials (CONSORT) flow chart of the trial is shown in Figure 1. The study is pre-registered at XYZ (no. 123). Hypotheses were specified in advance. This process included determining outcome scales, statistical models and cut-offs, time-points of evaluation, and publishing analysis scripts before the beginning of data collection. During the trial, we will follow Good Clinical Practice (GCP) and all quality- and safety aspects will be regularly monitored by an external party, the Karolinska Trial Alliance (i.e. case by case monitoring of informed consent, inclusion/exclusion criteria, source data quality, and adverse events). The study has been approved by the Swedish Ethical Review Authority (EPM 2022-01713-01) and Helse Bergen HF (no. 490097).

CONSORT 2010 Flow Diagram

[figure not shown]

Figure 1. CONSORT-flow diagram. Abbreviations: B4DT, Bergen 4-day treatment; CBT, cognitive behavior therapy.

Participants

Patients referred to one of the two involved OCD specialist clinics in Stockholm and self-referred patients will be assessed for eligibility by a staff clinician during a full psychiatric assessment. Candidates that live within approximately one hour of both clinics and match the inclusion/exclusion criteria (see Table 1) will be offered participation in the study and asked to provide informed consent.

Table 1. Overview of inclusion and exclusion criteria

Inclusion criteria	≥ 18 years of age.
	Primary diagnosis of OCD according to DSM-5.
	Clinician-rated Y-BOCS score of ≥ 16

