Patients in this arm will receive an intensive treatment delivered mostly in group format, the Bergen 4-day treatment (B4DT) [6]. The group sizes will be 3-6 participants with a 1:1 patient to therapist ratio. In the week leading up to the intensive part of the treatment, participants will have two scheduled phone/video calls with a therapist to assess readiness and encourage participants to prepare relevant exposure tasks. Day 1 of the intensive treatment includes psychoeducation about the rationale for exposure with response prevention (ERP), and deciding on exposure tasks. Days 2 and 3 focus on individually tailored and therapist-assisted ERP in as many relevant settings as possible (up to 7 hours of ERP per day). In the evenings, patients should continue with self-guided ERP and may receive therapist support via text messages or phone calls on demand. In the afternoon of day 3, patients can invite relatives and friends to a psychoeducation session. Day 4 of the intensive treatment focuses on treatment summary and relapse prevention, as well as planning self-guided ERP for the upcoming 3 weeks. After 14 weeks, participants have individual follow-up sessions at the clinic where they summarize their experiences after completing treatment. There is no ERP during this session.

All groups will be led by a therapist with expertise in B4DT. All therapists will have participated in the Norwegian OCD-training program [12] or have documented equivalent training. Prior to participation, all therapists will have participated in at least two B4DT groups.

Individual CBT

Patients will receive 16 90-minute sessions of individual CBT for OCD with an emphasis on ERP, delivered over a time period of 14 weeks according to a validated protocol [10]. Sessions will be held twice weekly at a specialist clinic during the first 2 weeks and once a week for the remaining 12 weeks. Sessions 1-2 contain psychoeducation about OCD and CBT, goal setting, and planning of ERP exercises. Sessions 3-14 include therapist-guided ERP (at the clinic, in the patients' homes or elsewhere as needed) with planned self-practice ERP between sessions. Sessions 15-16 contain a summary of the treatment and lessons learned, as well as relapse prevention and planning of continued self-practice ERP.

Therapist competence and adherence

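### Non-inferiority is declared from per-protocol complete cases alone, and intention-to-treat has no stated part in the conclusion

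*Combined protocol and SAP*

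**What the plan says.** The Y-BOCS paragraph under Statistical analysis, Primary outcome, specifies "ANCOVA of group differences at post-treatment with pre-treatment score as covariate". On the analysis set it says "It will be based on participants that have received at least 50% of the treatment", with thresholds of 8 CBT sessions or 1.5 B4DT days, "and completed the post treatment assessment 14 weeks after treatment start". Nothing is imputed at this stage. The stated reason for per protocol is to avoid bias towards non-inferiority.

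The decision rule is attached to that analysis: "Non-inferiority will be considered supported if the upper bound is less than 4 (the non-inferiority margin". The next paragraph adds: "For sensitivity assessment, the same ANCOVA model will be used again but with an intention to treat approach", with missing data estimated by maximum likelihood. No section says that this second analysis must meet the margin, or what is concluded if the two disagree.

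Two other sections matter. Study Design times every visit from treatment start: "Participants will be assessed before treatment start, at week 4 and 7, 14 weeks after treatment start (primary end-point". The Individual CBT section sets the pace of sessions: "Sessions will be held twice weekly at a specialist clinic during the first 2 weeks and once a week for the remaining 12 weeks".

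**The concern.** The plan's argument for per protocol is about dilution: non-adherence makes two arms look alike and so helps a non-inferiority claim. That is sound as far as it goes, but it does not cover selection after randomisation. Here the filter is arm-specific. A B4DT patient qualifies after a day and a half, a CBT patient only at session 8. Patients therefore leave the two analysed sets by different processes, and the remaining groups are no longer those that were randomised. Removing B4DT patients who left unimproved flatters B4DT; removing such CBT patients flatters CBT.

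Read literally, the rule declares non-inferiority when the per-protocol bound is below 4 even if the comparison of all randomised patients fails. Intention-to-treat can act as a check only if outcomes exist for patients below the threshold. A patient who never starts has no defined week-14 date, so that patient can enter only as an estimated value.

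**Working it through.** **Inputs from the documents** (Sample size calculation; Y-BOCS paragraph): 60 per arm, 10% missing, pre-treatment mean 22.6, CBT post-treatment mean 12.9, post-treatment SD 4.07, margin 4, two-sided 95% interval. The expected gain is 22.6 − 12.9 = 9.7 points.

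**Assumptions, not in the documents:** pre-post correlation r of 0.3 or 0.5; early-leaver proportions p_B (B4DT) and p_C (CBT); leavers' mean L. Differences are B4DT minus CBT, so positive values are worse for B4DT.

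**1. The plan's own power.** With 54 analysed per arm and r = 0, SE = 4.07 × √(2/54) = 0.783. Power ≈ Φ(4/0.783 − 1.98) = 99.9%. The stated figure of more than 95% is confirmed.

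**2. When the thresholds are reached.** Four CBT sessions fall in weeks 1–2, then one per week, so session 8 falls in week 6. In B4DT the threshold is passed on day 2.

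**3. What per protocol leaves out.** If the completers differ by d, then

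all-randomised difference = (1 − p_B) × d + (L − 12.9) × (p_B − p_C).

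With unimproved leavers (L = 22.6) the last term is about 1 point per 10 percentage points of difference in dropout. Setting the left side to 4 gives d = [4 − 9.7 × (p_B − p_C)] / (1 − p_B):

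- 5%/0% (B4DT/CBT): (4 − 0.485)/0.95 = 3.70
- 10%/0%: (4 − 0.97)/0.90 = 3.37
- 15%/5%: (4 − 0.97)/0.85 = 3.56
- 2%/15%: (4 + 1.261)/0.98 = 5.37

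**4. False non-inferiority under the per-protocol rule.** A hand check for 10%/0% with r = 0.3: residual SD = 4.07 × √(1 − 0.09) = 3.88; SE = 3.88 × √(1/54 + 1/60) = 0.728; probability ≈ Φ((4 − 3.37)/0.728 − 1.98) ≈ 13%. ANCOVA simulations (4,000–5,000 runs per setting) agree. The true all-randomised difference is 4 throughout, so 2.5% is nominal. The last two columns assume that every leaver is assessed at week 14.

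| Leavers B4DT/CBT | Per protocol, leavers unimproved | Per protocol, leavers get half the gain (L = 17.75) | Both sets required, leavers unimproved |
|---|---|---|---|
| 5%/0% | about 6% | 3.1% | 2.4% |
| 10%/0% | 14–17% | 3.3% | 2.9% |
| 15%/5% | 8–9% | 1.5–1.8% | 1.9–2.1% |

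With 2%/15% and unimproved leavers, the per-protocol rule gives about 0%. With equal dropout of 10%/10% it is conservative (0.3%).

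**5. Dependence on week-14 data.** The same three unimproved-leaver settings were repeated with the both-sets rule. If no leaver is assessed and their values are estimated from baseline alone, the error is about 5.4–13.6%, close to per protocol alone. If half are assessed, it is about 3.3–6.4%.

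**6. Power under the both-sets rule**, equal completers and unimproved leavers, all assessed:

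- 5%/5%: 99.8%
- 10%/10%: 99.4–99.7%
- 15%/5%: 91–94.5%
- 20%/10%: 88–91%

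In the two unbalanced cases the all-randomised difference is itself 9.7 × 0.10 = 0.97 points.

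**The case against.** **The documents lean towards more dropout in CBT, not B4DT.** The Introduction says that the long course of CBT raises dropout risk, and the Conclusion says that intensive formats may lower it. Day 1 of B4DT is psychoeducation, so the threshold falls early in the exposure work and a patient who leaves on day 3 stays in the set. If CBT does lose more patients, the per-protocol rule is conservative. This stands. A reader might infer that the plan is tilted towards B4DT; the documents do not support that. They also do not exclude it, since the dropout comparison has no directed hypothesis.

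**The inflation needs unimproved leavers.** This stands too: with half the gain, the error is close to nominal.

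**Intention-to-treat is pre-specified and a disagreement would be seen.** Dropout at the same thresholds is compared between arms, secondary outcomes use all randomised patients, dropout is monitored by arm, and CONSORT reporting is promised. So it would be wrong to say that there is no safeguard. But visibility is not a rule, and the published decision rule would still return non-inferiority. The analysis scripts are held outside the documents and could not be examined.

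**Never-starters can be included.** A reader might infer that intention-to-treat cannot place them at all. It can, through maximum likelihood. The gap is that they have no observation date. Patients who start and stop before 1.5 days do have one.

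**Conclusion.** The point holds as a gap in the decision rule, not as a demonstrated bias. Non-inferiority rests on a set selected after randomisation by thresholds that differ by arm, and a failing intention-to-treat result has no stated consequence.

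The size is conditional. At a true all-randomised difference of 4, false non-inferiority is roughly 6–14% (17% in one run) when B4DT loses 5–10 percentage points more patients and they do not improve. It is about 1.5–3.3% if they get half the gain, and about 0% at 2%/15%. Dropout rates, leaver outcomes and the pre-post correlation are all assumed.

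Requiring both sets brings the error back near 2.5% only if leavers are actually assessed, so the rule and the data collection belong together. The change is worth making, because the planned sample can carry it and it settles beforehand how a disagreement is read.

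**What to change.** 1. In the Y-BOCS paragraph, state: non-inferiority is concluded only if the upper 95% bound for B4DT minus CBT is below 4 in both the per-protocol and the intention-to-treat analysis; if the two disagree, the trial is reported as inconclusive on non-inferiority.
2. In Study Design and Measurements, state that the blinded week-14 Y-BOCS is sought from every randomised patient whatever treatment was received. For those who never start, time it from the planned first treatment day.

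The first change is SAP wording only. The second adds a visit-timing rule and the effort of following up patients who have left treatment; without it the first gives little protection. A claim can now fail on intention-to-treat. With balanced dropout of 5–10% and no true difference this costs under 1 point of power. That low cost does not carry over to unbalanced dropout: power is then about 91–94.5% (15%/5%) or 88–91% (20%/10%) with equal completers. Most of that loss reflects a real all-randomised difference of about 1 point rather than a penalty of the rule.

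### Superiority is decided on the per-protocol set, which the plan justifies only for non-inferiority, and ITT has no stated role in that decision

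*Combined protocol and SAP*

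**What the plan says.** All of the following is in the combined protocol and SAP.

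- **Analysis set** (Statistical analysis, Primary outcome, Y-BOCS). The ANCOVA covers patients who received at least half the treatment ("attended at least 8 sessions of individual CBT or 1.5 days of B4DT") and completed the week-14 assessment. Nothing is imputed.
- **Decision rule** (same section). Non-inferiority requires the upper bound to be below 4, and "superiority will be considered supported if the upper bound is less than 0". Both are read from the same interval.
- **Reason for the set** (same section). It is meant to avoid design problems that can "bias the results towards the alternative hypothesis of non-inferiority (the opposite is true in superiority trials").
- **Error claim** (same section). "This testing procedure has the Type I error rate controlled at the 2.5% level for both comparisons".
- **Role of ITT** (same section). "For sensitivity assessment, the same ANCOVA model will be used again but with an intention to treat approach". Its stated aim is to address non-random missing data in the per-protocol result. No rule covers disagreement between the two analyses.
- **Secondary outcomes** (Statistical analysis, Secondary outcomes). "Because the non-inferiority testing procedure will not apply, the secondary outcomes will be analyzed using an intent to treat approach including all randomized participants".
- **Contrast** (Y-BOCS section). "A 95% confidence interval will be used to model the gold standard CBT-B4DT effect".

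**The concern.** The superiority conclusion rests on a set chosen after randomisation, for a reason that applies to the other hypothesis. By the plan's own account the argument for per-protocol analysis does not carry over to superiority. Where the non-inferiority procedure does not apply, the plan goes to ITT.

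The documents also leave room for exclusion to differ between arms:

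- The attendance rule is the complement of the dropout definition (Statistical analysis, Dropout rate). Whether that dropout differs by arm is a secondary question with no directed hypothesis.
- With full attendance, the threshold is reached on day 2 in B4DT. In CBT it is reached in week 6: two sessions a week for 2 weeks give 4, and four weekly sessions give 8. Exclusion therefore arises over very different periods.
- The arms are delivered at different clinics, and the Limitations section plans to examine travel distance as a cause of dropout.

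A superiority claim could therefore partly reflect who was left out. Equally, a real advantage could be missed. What is at stake is the follow-on superiority claim. It belongs to the primary-outcome sequence and is not covered by the caution attached to secondary analyses.

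**Working it through.** **Inputs from the documents.** 60 per arm, post-treatment SD 4.07 (CBT arm), 10% missing, margin 4 (Sample size calculation); two-sided 95% interval.

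**Assumptions.** Exclusion rates by arm, outcomes of excluded patients and the pre-post correlation are not given. The contrast is B4DT minus CBT, as the decision rule requires when lower Y-BOCS is better. Error means claiming superiority when all randomised patients in the two arms have equal means.

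**1. The plan's own figure.** With 54 evaluable per arm (60 × 0.9) and no credit for the baseline covariate, SE = 4.07 × √(2/54) = 0.783. Non-inferiority power at no difference is Φ(4/0.783 − 1.96), about 99.9%, consistent with the stated figure above 95%.

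**2. From exclusion to shift.** If excluded patients differ from included ones by D points in both arms and the ITT means are equal, the per-protocol contrast moves by (exclusion gap) × D. A gap of 10 percentage points (6 of 60 patients) and D = 5 (5/4.07 = 1.2 SD) gives 0.5 points. The same gap with D = 2.5 gives 0.25. A gap of 5 points (3 of 60) with D = 2.5 gives 0.125.

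**3. Superiority error, closed form.** Error = Φ(−1.96 + s/0.783), where s is the net shift favouring B4DT.

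| s (points) | Error |
|---|---|
| +0.5 | 9.3% |
| +0.25 | 5.0% |
| +0.125 | 3.6% |
| 0 | 2.5% |
| −0.25 | 1.1% |
| −0.5 | 0.5% |

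With an assumed pre-post correlation of 0.5 (SE 0.678), s = +0.5 gives 11.1% and s = −0.5 gives 0.35%.

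**4. Power at an assumed true 2-point advantage.** Without selection: Φ(2/0.783 − 1.96) = 72%. With s = −0.5: Φ(1.5/0.783 − 1.96) = 48%.

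**5. ANCOVA simulation.** 20,000 trials per scenario, 60 per arm, SD 4.07, assumed correlation 0.3, equal ITT means.

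| Excluded, B4DT / CBT | Excluded patients' outcome | Per-protocol error |
|---|---|---|
| 10% / 10% | same | 2.7% |
| 10% / 10% | 5 points worse | 2.3% |
| 15% / 5% | 5 points worse | 9.7% |
| 15% / 5% | 2.5 points worse | 5.0% |
| 5% / 15% | 5 points worse | 0.4% |
| 5% / 15% | 2.5 points worse | 1.1% |
| 5% / 15% | 5 points better | 9.6% |
| 5% / 15% | 2.5 points better | 5.4% |
| 15% / 5% | 5 points better | 0.3% |

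ITT with every week-14 outcome observed gives 2.3% to 2.6% throughout. At a true 2-point advantage with 5% / 15% excluded and 5 points worse, power is 51% per protocol and 74% under ITT. The two disagree on superiority in 25% of trials.

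**6. ITT when week 14 is also missed.** Likelihood analysis with weeks 4 and 7 included: 4,000 trials, normal approximation, assumed correlations with week 14 of 0.5 and 0.65, and interim shifts of 50% and 80% of the week-14 shift. With 15% / 5% excluded and 5 points worse, the error is 3.5% (bias 0.11) if half of the excluded miss week 14, and 5.2% (bias 0.25) if all do. ITT then reduces the problem but does not remove it.

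**The case against.** The strongest reply has four parts.

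1. **An ITT result will exist.** The same ANCOVA is refitted under ITT, so its bound can be compared with 0. The Limitations section also monitors dropout in both arms. This stands, but the weight of the ITT result is not stated, and the dropout check concerns travel distance. The plan also says "All analysis scripts have been uploaded to a public repository with the analysis strategies described in detail using simulated data". Those scripts were not among the documents reviewed, and they may say more.
2. **Superiority is inside the non-inferiority procedure.** On that reading, using ITT only for secondary outcomes is not inconsistent, and the remark about superiority trials may mean only that design problems push such trials towards no difference. This is a fair reading of the wording. It still supplies no reason for deciding superiority on the per-protocol set.
3. **The likely direction is conservative.** The Introduction links the long CBT format to dropout. If more CBT patients are excluded and they do worse, the error falls to about 0.4% to 1.1%. This stands. The price is then lost power, and the documents do not show whether excluded patients would do worse or better.
4. **The larger figures need strong inputs.** Errors of 9% to 10% require a gap of 6 of 60 patients and a 1.2 SD difference. A gap of 3 patients at 2.5 points gives 3.6%. This also stands, and the figures should be read as a range.

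The abstract's hypothesis, the power calculation and the conclusion all concern non-inferiority, which limits the seriousness.

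**Conclusion.** The concern holds. The plan decides superiority on a set that it justifies for non-inferiority only, gives ITT no part in that decision, and states a 2.5% error that nesting alone does not secure. High confidence applies to this reading of the text, not to the size or direction of any bias.

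Under assumed exclusion gaps of 10 percentage points and outcome differences of 2.5 to 5 points, the superiority error runs from about 0.3% to 9.7%. It stays near 2.5% when exclusion is unrelated to outcome or equally informative in both arms. The decision should be changed before results are seen. The non-inferiority set, margin and sample size are not challenged.

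**What to change.** 1. State that, once non-inferiority is supported on the per-protocol set, superiority is decided on ITT: all randomised patients, with every available week-14 Y-BOCS regardless of attendance. Keep per-protocol as supportive. This is the essential change.
2. Include the week-4 and week-7 Y-BOCS in that likelihood analysis, unless the public scripts already do. The plan's doubt about imputing from past observations is raised for secondary outcomes; the Y-BOCS has two interim assessments.
3. Limit the 2.5% sentence to multiplicity across the two nested tests, conditional on the analysis-set and missing-data assumptions.
4. Report the ITT upper bound against 4 beside the per-protocol result, and call non-inferiority not robust if they disagree. This goes beyond the superiority point but uses the same output.
5. Reconcile the contrast label with the decision rule. Read as CBT minus B4DT, an upper bound below 0 would favour CBT; the rule needs B4DT minus CBT.

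The cost is a few SAP sentences and at most a small script change. No visit is added. Superiority becomes slightly harder to claim if selection favours B4DT, and easier if it favours CBT. Bias from missed week-14 assessments is reduced, not removed.
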